3.1 Baseline Definition

For all endpoints the baseline value will be the latest before test product or positive control product for subjects randomised to the test regimen and positive control regimen, and before baseline cleansing for subjects randomised to the untreated regimen.

3.2 Subgroups/Stratifications

Eligible subjects will be stratified by age (<21 years, ≥21 years) when randomised into treatments. There are therefore two strata in this study:

- Stratum1: Subjects of age<21 years;
- Stratum2: Subjects of age ≥21 years.

3.3 Timepoints and Visit Windows

Deviations from the scheduled assessment times should be avoided or kept to a minimum as possible. Any deviation will be noted in the blinded data review before database lock and subjects may be considered for exclusion from the per protocol population.

The following are the assessment time windows.

Visit	Time window
Visit 2	5-7 days after Visit 1. Visit 2 is baseline and counted as Day 1.
Visit 3	Day 8 ± 1 Day

Visit	Time window
Visit 4	$Day 29 \pm 2 Days$
Visit 5	Day 57 ± 2 Days

Acute corneometer assessments will be taken 1 hour \pm 15 MINUTES, 3 hours \pm 15 MINUTES and 8 hours \pm 15 MINUTES after application of the cream for subjects randomised to the test product and positive control regimens and after cleansing for subjects randomised to the untreated regimen.

Sebumeter kinetic measurements will be taken 5 ± 1 minutes and 90 ± 5 minutes after forehead cleansing.

4 Data Analysis

Data analysis will be performed by inVentiv Health Clinical. Prior to database closure a Blind Data Review Meeting (BDRM) will be conducted in which various aspects of the trial will be discussed and agreed. The statistical analysis software used will be SAS version 9.4.

Unless otherwise described below, all listings will be produced for all randomized subjects.

4.1 Populations for Analysis

Tables described in this section will be produced for all randomised subjects, unless otherwise specified.

4.1.1 Subject Disposition

Screen failures will be defined as subjects who consent to participate in the study but are never subsequently randomised. A summary will be provided of the number of subjects screened and the number of screen failures.

Subject disposition will be summarised as the number and percentage of subjects (out of the number of randomised subjects) who complete the study, with the number who discontinue broken down by reason for discontinuation (Table 14.1.1). The table will also summarise the number and percent of subjects assigned to each analysis population (defined in Section 2.1.3). The summary will be presented by treatment and overall.

Subject disposition will be listed for randomised subjects (Listing 16.2.1.1) and non-randomised subjects (Listing 16.2.1.2) separately.

4.1.2 Protocol Deviations

Protocol deviations will be tracked by the study team throughout the conduct of the study. All deviations will be reviewed prior to unblinding and closure of the database to ensure all important violations are captured and categorised.

Major deviations identified as liable to influence the efficacy outcome will include follows:

- Deviation from the inclusion/exclusion criteria
- Use of prohibited medication
- Not receiving randomised treatment

Further deviations liable to influence the efficacy outcome will be given in the "Review Listing Requirement (RLR)" document and major deviations will be identified in blinded data review stage. The number and percentage of subjects with any major protocol deviations and with each type of major protocol deviations will be presented by treatment (Table 14.1.2) and listed (Listing 16.2.2.1). Any minor protocol deviations will be listed similarly (Listing 16.2.2.2).

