6.3.2. Diary Review (Compliance)

Subject diaries will be reviewed by the Investigator or their designee. The total number of missed and additional standard cleanser, positive control cleanser, test product and/or positive control applications, as appropriate per subject randomisation, will be recorded on the eCRF. Subjects who apply each of their allocated products

Document Name	Rainbow Clinical Protocol.doc		
Туре	Version	Document Identifier	Effective Date
eldo controlled	4.0; Most-Recent; Effective; CURRENT	090032d580d464b0	23-May-2017 08:33:00
Reason For Issue	Auto Issue		

more or less frequently than twice a day will be considered to have deviated from the protocol and additional/missed applications will recorded on the Deviations Log on the eCRF.

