9.2.1. Definition of Analysis Populations

The 'Intent to treat' (ITT) population includes all subjects who are randomised into the study and have at least one post-baseline measurement available. All efficacy analyses will be based on the ITT population.

The Per Protocol (PP) population will consist of the subset of ITT subjects which excludes those subjects with significant protocol deviations. Protocol deviations will

Document Name	Rainbow Clinical Protocol.doc		
Туре	Version	Document Identifier	Effective Date
eldo controlled	4.0; Most-Recent; Effective; CURRENT	090032d580d464b0	23-May-2017 08:33:00
Reason For Issue	Auto Issue		

be identified prior to database unblinding and will include, but not be limited to, non-compliance with the protocol or product application and use of prohibited concomitant medications. Confirmatory analyses of at least the primary efficacy endpoint will be performed on the PP population.

The Safety population will include all subjects who applied any of the study products. All safety analyses will be performed using the Safety population. For the no treatment regimen, this will include any use of the cleanser post-randomisation.

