4.3 Treatments (Study Product, Rescue Medication, other Concomitant Therapies, Compliance)

4.3.1 Study Product Compliance and Exposure

Study product compliance (using study products twice daily) will be listed (Listing 16.2.5.1) and checked at the blinded data review stage for evaluation of protocol violations. A compliance summary table will be provided for ITT population (Table 14.2.1).

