AGE (YEARS)				
n	XX	XX	xx	XX
MEAN	XX.X	XX.X	xx.x	XX.X
SD	XX.XX	XX.XX	xx.xx	XX.XX
MEDIAN	XX.X	XX.X	xx.x	XX.X
MINIMUM	XX	XX	XX	XX

207196

Statistical Reporting and Analysis plan, 19 Sep 2017

	Test Product (N=XX)	Untreated (N=XX)	Positive Control (N=XX)	Overall (N=XX)
MAXIMUM	XX	XX	XX	XX
FITZPATRICK SCALE FOR SKIN T	TYPE			
I	xx (xx.x)	xx (xx.x)	xx (xx.x)	xx (xx.x)
II	xx (xx.x)	xx (xx.x)	xx (xx.x)	xx (xx.x)
III	xx (xx.x)	xx (xx.x)	xx (xx.x)	xx (xx.x)
IV	xx (xx.x)	xx (xx.x)	xx (xx.x)	xx (xx.x)
V	xx (xx.x)	xx (xx.x)	xx (xx.x)	xx (xx.x)
VI	xx (xx.x)	xx (xx.x)	xx (xx.x)	xx (xx.x)
AGE STRATA (By Planned Rando	omisation)			
Age < 21	xx (xx.x)	xx (xx.x)	xx (xx.x)	xx (xx.x)
Age ≥ 21	xx (xx.x)	xx (xx.x)	xx (xx.x)	xx (xx.x)
AGE STRATA (By Actual Age)				
Age < 21	xx (xx.x)	xx (xx.x)	xx (xx.x)	xx (xx.x)
Age ≥ 21	xx (xx.x)	xx (xx.x)	xx (xx.x)	xx (xx.x)

Fitzpatrick Scale I: Always burns, never tans II: Usually burns, tans minimally III: Sometimes mild burn, tans uniformly (cream white; fair with any hair or eye color) IV: Burns minimally, always tans well (moderate brown) V: very rarely burns, tans very easily (dark brown). VI Never burns, never tans (deeply pigmented dark brown to darkest brown).

Page x of y

PPD

207196

Statistical Reporting and Analysis plan, 19 Sep 2017

Protocol 207196 Program Run Date:xxxx

Table 14.2.1 Compliance* Intent-to-Treat Population

Intent-to-Treat Population(N=XX)

Compliance Period	Product	Test product (N=XX)	Untreated (N=XX)	Positive Control (N=XX)
V2 to V3	Cream Cleanser	MEAN (SD) Median (MIN, MAX) x.xx(x.xxx) x.xx(x.xx, x.xx) x.xx(x.xxx) x.xx(x.xx, x.xx)	MEAN (SD) Median (MIN, MAX) x.xx(x.xxx) x.xx(x.xx, x.xx)	MEAN (SD) Median (MIN, MAX) x.xx(x.xxx) x.xx(x.xx, x.xx) x.xx(x.xxx) x.xx(x.xx, x.xx)
V3 to V4	Cream Cleanser			
V4 to V5	Cream Cleanser			

^{*}Compliance = Actual Number of Uses / Expected Number of Uses

Page x of y

PPD

Programming Note: For each subject, Total Expected = 2*Number of Days Between the Two Visits; Actual Uses = Expected Number - Missed Uses + Extra Uses. For untreated group, only cleasner row to be filled.

Program Run Date:xxxx Protocol 207196

Table 14.2.2.1 Analysis of Corneometer Change from Baseline Intent-to-Treat Population

Intent-to-Treat Popula	tion	(N=XX)	
------------------------	------	--------	--

Visit		Variable	Test Product	Untreated	Positive Control
			(N=XX)	(N=XX)	(N=XX)
1 Hour Change from Baseline					

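### The blinded review that sets per-protocol exclusions is sent a compliance listing by product, which separates untreated subjects from cream users

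*SAP*

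**What the plan says.** Both documents want per-protocol exclusions settled without knowledge of treatment. Protocol 9.2.1 says that protocol deviations will "be identified prior to database unblinding and will include, but not be limited to, non-compliance with the protocol or product application". SAP 4.1.2 adds "All deviations will be reviewed prior to unblinding and closure of the database", and "major deviations will be identified in blinded data review stage". SAP section 4 places a Blind Data Review Meeting before database closure, and SAP 2.2 distributes the randomisation codes only after lock.

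The same SAP 4.1.2 names three major deviations, one of which is "Not receiving randomised treatment". It leaves further deviations to a separate Review Listing Requirement document. Under SAP 4.1.3, a major deviation removes a subject from the per-protocol population, on which corneometry and blemish count are re-analysed.

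On compliance, SAP 4.3.1 says that use of study product is put in Listing 16.2.5.1 and "checked at the blinded data review stage for evaluation of protocol violations". Protocol 6.3.2 describes the source data: missed and extra uses of each cleanser, "test product and/or positive control applications, as appropriate per subject randomisation, will be recorded on the eCRF". In SAP Attachment 2, the programming note to Table 14.2.1 reads "For untreated group, only cleasner row to be filled".

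**The concern.** A blinded review protects the per-protocol set only if those deciding exclusions cannot see the arm. Here the SAP directs them to a listing whose pattern of entries carries allocation. No cream entry means the subject is untreated.

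The review also has some discretion. SAP 3.3 says that subjects with timing deviations may be considered for exclusion, and the shells for Table 14.1.3 and Listing 16.2.2.1 allow exclusion by visit or time. If reviewers can tell untreated from treated subjects while making such calls, exclusions can differ by arm, even without intent. What is at stake is the credibility of the per-protocol analyses, which Protocol 9.2.1 describes as confirmatory for at least the primary endpoint.

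**Working it through.** The plan states no figure on this point, so there is none to reproduce. The check sets the texts side by side and maps product entries to arms.

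**1. What the review receives.** For medical history (SAP 4.2.2) and for prior and concomitant medication (SAP 4.3.2), the SAP says a further data listing is produced for the blinded review. For compliance (SAP 4.3.1) it mentions no further listing. Listing 16.2.5.1 itself is what gets checked.

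**2. What that listing shows.** Its shell in SAP Attachment 2 has a Product column with the numbers of missed and extra uses. The shell also carries a treatment-group heading. Assume that heading is removed for a blinded review, which is the reading most favourable to the plan. The Product column remains.

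**3. What the product entries reveal.** The arms are those of Protocol 6.2.12 and 6.3.2. The generic labels are those of Table 14.2.1.

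| Arm | Products named as on the eCRF | Generic labels |
|---|---|---|
| No treatment | standard cleanser | Cleanser |
| Test product | standard cleanser + test product | Cleanser + Cream |
| Positive control | positive control cleanser + positive control cream | Cleanser + Cream |

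With named products, the three sets are all different, so every arm is identifiable. With generic labels, the untreated arm is still unique, while test and positive control look alike.

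**4. How many subjects.** The plan randomises 132. The allocation ratio is not stated; equal allocation is assumed because about 40 completers are planned in each arm.
- Untreated: 132 / 3 = 44.
- On a cream: 132 − 44 = 88.
- Generic labels: about 44 are known to be untreated, and about 88 are known to be on a cream without knowing which.
- Named products: all 132 are identifiable by arm.

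The primary comparison is test product against no treatment. Even the generic layout therefore exposes one side of it exactly and places the other side among the cream users.

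**5. The treatment-received criterion.** Someone must compare assigned with received product to judge this deviation. That person need not sit on the review. Protocol 5.7.2 allows site staff outside the outcome procedures to know allocation, and Protocol 6.2.12 and 6.2.13 have such staff dispense products and supervise use. A yes/no flag from an unblinded person would tell reviewers nothing about arm. The SAP does not say that the information arrives in this way.

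**The case against.** Several points on the other side stand.

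- A reader might infer that the blind is broken before exclusions are decided. The documents do not show that. They place the review before unblinding and code release, and they do not say who attends or how its listings are masked. The Review Listing Requirement document is not among those reviewed. Attachment 2 holds templates for study report outputs, so the review may see a different format.
- A reader might infer that all 132 subjects are necessarily exposed. That holds only if products are named. The contents of the Product column are not specified, and Table 14.2.1 uses generic labels.
- A reader might infer that judging "Not receiving randomised treatment" must unblind the review. A flag from unblinded staff avoids this, and the criterion may also cover subjects who received nothing.
- The primary endpoint is read 8 hours after the first, supervised application. Later diary compliance cannot alter that reading, and exclusion by visit would let a later lapse leave the Day 1 result in place.
- All efficacy analyses are based on ITT (Protocol 9.2.1). P-values are treated mainly as summary statistics in this proof-of-concept study.

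Two things remain. SAP 4.3.1 names the product-level listing and describes no masking, although the SAP adds a review listing for other data. And knowledge of arm gained from compliance data can carry over to other judgements, including whether a Day 1 timing deviation leads to exclusion. That would affect the primary endpoint's per-protocol analysis.

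**Conclusion.** The point holds as a gap in how the SAP keeps its review blind. As written, the compliance listing sent to the review distinguishes untreated subjects from cream users, and it distinguishes all three arms if products are named. The counts of about 44 and 88 rest on equal allocation of 132 subjects.

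The consequence is limited to membership of the per-protocol population, and so to the supportive analyses of corneometry and blemish count. The ITT analyses do not change. Evaluators are kept from allocation and diaries by Protocol 5.7.2, and this review does not affect that. The size of any bias cannot be derived, because the documents do not say how many subjects would be excluded, from which arm, or with what outcomes. The change is worth making because it is cheap and gives the review the blinding that the SAP claims for it.

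**What to change.** **SAP 4.3.1.** Replace Listing 16.2.5.1 at the review with one product-neutral compliance figure per subject and visit interval. Take it from the cleanser entries that all three arms have, labelled only as cleanser. Apply the same masking to any deviation-log entries on missed or extra uses that name a product. Judge cream compliance by a numeric cut-off written into the Review Listing Requirement document before the review. Apply it by rule before database closure and after the review's other exclusions are recorded, because a cream flag would itself show that the subject is on a cream.

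**SAP 4.1.2.** State that someone outside the review who is already unblinded compares the dispensing records with the randomisation schedule. That person supplies the treatment-received deviation as a yes/no flag before database closure, which keeps the SAP's rule that deviations are reviewed before unblinding and closure.

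**Cost.** SAP wording and one modified listing, with no new data or subjects. The small downside is that cream compliance is no longer judged case by case.

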4.1.3 Analysis Populations

Six analysis populations are defined.

Population	Definition / Criteria	Analyses Evaluated
All Screened	All subjects those who are screened	Disposition
Subjects		
Randomised	All subjects who are randomised and may or	Protocol deviations
	may not receive the application of the study	
	products.	
Safety	Safety population includes all subjects who	Safety analysis
	are randomised and receive at least one dose	
	of study product. For the no-treatment	
	regimen, this will include any use of the	
	cleanser post-randomisation.	
Intent-to-Treat	The 'Intent to treat' (ITT) population	Efficacy analysis
(ITT)	includes all subjects who are in safety	
	population and have at least one post	
	baseline efficacy assessment.	
Per-Protocol	The Per Protocol (PP) population will consist	Efficacy analyses for
(PP)	of the subset of ITT subjects which excludes	corneometry and
	those subjects with major protocol	blemish count will also
	deviations.	be performed on the PP
		population

The numbers of subjects included in each of the analysis populations, and the number excluded from each population broken down by the reason for exclusion will be presented (Table 14.1.3). Subjects excluded from any of the analysis populations will be listed (Listing 16.2.3.1).

4.2 Subject Demographics and Other Baseline Characteristics

4.2.1 Demographic Characteristics

Categorical demographic variables include sex, race and Fitzpatrick type. These variables will be summarised by the number and percentage of subjects with each relevant characteristic (Table 14.1.4.1 for the Safety population, Table 14.1.4.2 for the ITT population and Table 14.1.4.3 for the PP population). Age will be summarised by the mean, standard deviation (SD), median, minimum and maximum values. Baseline stratification will also be summarised by the number and percentage of subjects in each stratum. All summaries will be presented by treatment, and overall. All demographic information will be listed (Listing 16.2.4.1).

4.2.2 General Medical History

Medical history data will be listed in Listing 16.2.4.2 with start date and end date or ongoing at the start of study drug. A data listing will also be produced for evaluation of protocol violations at the blinded data review stage.

4.3 Treatments (Study Product, Rescue Medication, other Concomitant Therapies, Compliance)

4.3.1 Study Product Compliance and Exposure

Study product compliance (using study products twice daily) will be listed (Listing 16.2.5.1) and checked at the blinded data review stage for evaluation of protocol violations. A compliance summary table will be provided for ITT population (Table 14.2.1).

4.3.2 Prior and Concomitant Medication

Prior and concomitant medication/non-drug treatments data will be listed (Listing 16.2.5.2, 16.2.5.3). Prior medications are defined as those stopped before the baseline administration of the study products. Concomitant medications are defined as those ongoing or started on or after the baseline administration of the study products.

A data listing will also be produced for evaluation of protocol violations at the blinded data review stage.

4.4 Analysis of Efficacy

Statistical testing of all endpoints in this study will be conducted at unadjusted two-sided significance level of 0.05. The null and alternative hypotheses are

- H₀: there is no difference between treatment groups;
- H_a: there is a difference between treatment groups.

While for this proof of concept study statistical significance (p<0.05) may not be achieved, these results will drive sample size projections for future studies. Due to the exploratory nature of the study, no adjustment to the alpha level for multiple comparisons will be made. P-values resulting from inferential testing will be considered primarily as summary statistics.

No statistical comparisons between the positive control regimen and the test product regimen are planned. The positive control is included to provide internal validation to the trial and to provide a reference point for estimates of effect size.

4.4.1 Primary Efficacy Endpoint

4.4.1.1 Primary Efficacy Endpoint Definition

The corneometer measurement of each subject at each assessment point will be calculated as the mean of the three repeated measurements of the subject at that assessment point.

The primary endpoint is the change from baseline in Corneometer measurement at 8 hours following the first product application. Data for the endpoint will be summarized by age stratum and treatment regimen (Table 14.2.2.2, 14.2.2.3 for the ITT population and Table 14.2.2.5, 14.2.2.6 for the PP population).

4.4.1.2 Statistical Hypothesis, Model, and Method of Analysis

Analysis of covariance (ANCOVA) will be applied with treatment as main effect, age stratification and baseline measurement as covariate. Least squares means and differences between least squares means for (i) test product and no treatment regimen; (ii) positive control and no treatment regimen will be presented, together with 95% confidence intervals (Table 14.2.2.1 for the ITT population, Table 14.2.2.4 for the PP population).

In the randomisation stage of the study, a substantial number of subjects were randomised using wrong age stratum randomisation scheme. In all summary and analyses involving age stratum, subjects will be assigned to correct age strata using their actual ages.

4.4.1.3 Supportive Analyses

The normality assumption for ANCOVA in primary analysis will be checked. If violated, non-parametric method such as Wilcoxon rank sum test may be applied.

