9. STATISTICAL CONSIDERATIONS AND DATA ANALYSES

9.1 Sample Size Determination

Approximately 200 female subjects aged 18-45 with self-assessed sensitive skin and a minimum of $10 \ 8$ and a maximum of 25 facial blemishes (papules and pustules, excluding the nose) will be screened to randomise 132 healthy subjects, to ensure approximately 40 subjects in the test product regimen, 40 subjects in the no treatment regimen and 40 subjects in the positive control regimen complete the study (Assuming a 10% dropout rate). Randomisation will be stratified by age (<21 years old, ≥ 21 years of age).

The sample size was based on clinical considerations. In a previous study of a cosmetic product, counts of papules and pustules decreased from a baseline mean of 27.6 to a mean of 13.5 at Week 8 (ref. Shalita 1995 IJD). With 40 subjects in both the test product and no-treatment regimens, a difference between groups at least 60% the magnitude of the standard deviation (assumed equal for both groups) would be detectable at two-sided alpha=0.05 with approximately 80% power.

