9.3.2. Primary Analysis(es)

The primary endpoint is the change from baseline in Corneometer measurement at 8 hours following the first product application (use of cleanser for the no treatment regimen). Data for the endpoint will be summarized by age stratum and treatment

Document Name	Rainbow Clinical Protocol.doc		
Туре	Version	Document Identifier	Effective Date
eldo controlled	4.0; Most-Recent; Effective; CURRENT	090032d580d464b0	23-May-2017 08:33:00
Reason For Issue	Auto Issue		

regimen using means and 95% confidence intervals and compared between treatment regimens using analysis of covariance (ANCOVA) with treatment main effect, age stratum (<21, ≥21 years of age) and baseline measurement as covariate or Wilcoxon rank sum test, depending on the data distribution. Differences between least squares means for the test product and no treatment regimen will be presented, together with 95% confidence intervals.

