		LSmeans(SE), p-value[1]	X.xx(x.xxx), 0.xxxx	X.xx(x.xxx), 0.xxxx	X.xx (x.xxx), 0.xxxx
		Comparison[1][2]	Difference	95%CI	P-value
		Test vs Untreat	x.xx	(x.xx, x.xx)	0.xxxx
		Positive v Untreat	x.xx	(x.xx, x.xx)	0.xxxx
3 Hours Change from Baseline	(same template)				
8 Hours Change from Baseline	(Same template)				
1 Week Change from Baseline	(Same template)				
4 Week Change from Baseline	(Same template)				
8 Week Change from Baseline	(Same template)				

^[1] From ANCOVA with treatment main effect, age stratum and baseline as covariate

[2] Difference is first named treatment minus second named treatment such that a negative difference favours the first named treatment

Page x of y

PPD

Programming Note: If non-parametric method is used due to the failure in ANCOVA model check, the following non-parametric results should be added to the table

Comparison	P-value (Wilcoxon)
Test vs. Untreat	A yeary
Positive vs Untreat	0.xxxx 0.xxxx

Protocol 207196 Program Run Date:xxxx

Table 14.2.2.2

Summary of Corneometer Change from Baseline
Intent-to-Treat Population

Intent-to-Treat Population(N=XX)

Visit	Variable	Test Product	Untreated	Positive Control
		(N=XX)	(N=XX)	(N=XX)
Baseline	n	Xx	Xx	Xx
	MEAN	x.xx	x.xx	x.xx
	SD	x.xxx	x.xxx	x.xxx
	MEDIAN	x.xx	x.xx	x.xx
	MINIMUM	X.xx	X.xx	X.xx
	MAXIMUM	X.xx	X.xx	X.xx
1 Hour				
	n	Xx	Xx	Xx
	MEAN	x.xx	x.xx	x.xx
	SD	x.xxx	x.xxx	x.xxx
	MEDIAN	x.x	x.x	x.x
	MINIMUM	X.x	X.x	X.x
	MAXIMUM	X.x	X.x	X.x
1 Hour Change from Baseline				
	n	Xx	Xx	Xx
	MEAN	x.xx	x.xx	x.xx
	SD	x.xxx	x.xxx	x.xxx

GlaxoSmithKline Consumer Healthcare Confidential

CC

207196

Statistical Reporting and Analysis plan, 19 Sep 2017

Visit		Variable	Test Product	Untreated	Positive Control
			(N=XX)	(N=XX)	(N=XX)
		MEDIAN	x.x	x.x	x.x
		MINIMUM	X. x	X.x	X.x
		MAXIMUM	X.x	X.x	X.x
3 Hours	(same template)				
3 Hours Change from Baseline	(same template)				
8 Hours	(same template)				
8 Hours Change from Baseline	(Same template)				
1 Week	(Same template)				
1 Week Change from Baseline	(Same template)				
4 Week	(Same template)				
4 Week Change from Baseline	(Same template)				
8 Week	(Same template)				
8 Week Change from Baseline	(Same template)				

Page x of y

PPD

Protocol 207196 Program Run Date:xxxx

Table 14.2.2.3

Summary of Corneometer Change from Baseline by Age Strata
Intent-to-Treat Population

Intent-to-Treat Population (N=XX)

Visit	Stratum	Variable	Test Product	Untreated (N=XX)	Positive Control (N=XX)
			(N=XX)		
Baseline	Age<21	n	Xx	Xx	Xx

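### The only fallback named for non-normal data is an unadjusted rank sum test; rank ANCOVA would keep the baseline and age-stratum adjustment

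*SAP*

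**What the plan says.** The primary endpoint is change from baseline in the corneometer reading 8 hours after first application. SAP 4.4.1.2 analyses it by ANCOVA with treatment, age stratum and baseline, and reports least squares mean differences with 95% CIs. It also records that a sizeable number of subjects were randomised from the wrong age-stratum schedule, and that analyses involving stratum will use actual age.

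The fallback is described in four places, and they do not quite agree:

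- **Protocol 9.3.2 (primary)** offers ANCOVA with "baseline measurement as covariate or Wilcoxon rank sum test, depending on the data distribution". It then says, without condition, that least squares mean differences and 95% CIs will be shown.
- **Protocol 9.3.3 (secondary)** makes the Wilcoxon test an optional addition to ANCOVA.
- **SAP 4.4.1.3 (Supportive Analyses)** says "If violated, non-parametric method such as Wilcoxon rank sum test may be applied". SAP 4.5.1 uses the same wording for the later corneometer readings, sebumetry, sebum excretion rate and blemish counts.
- **SAP Attachment 2, Table 14.2.2.1** has a programming note that puts Wilcoxon p-values into the table that already holds the ANCOVA differences, CIs and p-values. The added rows contain a p-value only.

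No normality test or threshold is given, and no sentence says which result leads when the two are both present.

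**The concern.** The main model adjusts for two things: the baseline reading and the age stratum used in randomisation. The one fallback named adjusts for neither, apart from working on the change score. Subtracting baseline is not the same as adjusting for it. Unless baseline and post-treatment values are very highly correlated, the change score carries baseline noise that a covariate would remove, and the test loses power.

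The age stratum deserves attention here because of the randomisation errors. Balance on actual age can no longer be taken from the stratified schedule, and the SAP's answer is to use actual age in the analysis. A plain rank sum test bypasses that answer.

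At stake is the power and the adjustment of the fallback test for the primary endpoint and for every secondary continuous endpoint. Non-normality is most plausible for the blemish counts, which are small integers: the screening total of 8 to 25, spread over two lesion types and three facial areas, averages 8/6 = 1.3 to 25/6 = 4.2 per cell.

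**Working it through.** **Inputs from the documents.** Alpha: "Statistical testing of all endpoints in this study will be conducted at unadjusted two-sided significance level of 0.05" (SAP 4.4). Group size: "With 40 subjects in both the test product and no-treatment regimens" (Protocol 9.1). Effect: 0.6 of a common SD (Protocol 9.1). The documents do not say whether that SD is of the change or of the post-treatment value; it is taken here as the SD of change.

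**Inputs assumed, because the documents give none.** Baseline-to-post correlation ρ of 0.3, 0.5, 0.7 or 0.9; normal, lognormal or t(3) errors; normally distributed baseline; 30% of subjects under 21; no age effect on outcome.

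**Step 1: the plan's own figure.** Protocol 9.1 claims detection "at two-sided alpha=0.05 with approximately 80% power". Normal approximation: 0.6 × √(40/2) = 2.683; 2.683 − 1.960 = 0.723; Φ(0.723) = 76.5%. The two-sample t test gives 75.5%. With 132/3 = 44 randomised per arm: 0.6 × √(44/2) = 2.814; 2.814 − 1.960 = 0.854; Φ(0.854) = 80.3%. The stated 80% therefore matches the number randomised, not the 40 completers. That is a separate matter and does not affect the comparison below.

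**Step 2: why the covariate matters.** With equal variances σ², the change score has variance 2(1 − ρ)σ². After adjustment for baseline the variance is (1 − ρ²)σ². The ratio is (1 + ρ)/2, which is 0.65, 0.75, 0.85 and 0.95 for ρ = 0.3, 0.5, 0.7 and 0.9. The benefit of adjusting is large at low correlation and nearly gone at 0.9.

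**Step 3: closed-form check under normality.** The Wilcoxon test has relative efficiency 3/π = 0.955, so its power is Φ(0.6 × √(40 × 0.955/2) − 1.960) = Φ(0.662) = 74.6%. This is close to the simulated 71.9 to 74.0%.

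**Step 4: simulation.** Two arms of 40, 4,000 trials per cell. Rank ANCOVA regresses ranked change on treatment, ranked baseline and age stratum. The Wilcoxon test is applied to the change. Power (%) at 0.6 SD:

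| Errors | ρ | ANCOVA | Wilcoxon | Rank ANCOVA | Gain over Wilcoxon |
|---|---|---|---|---|---|
| Lognormal | 0.3 | 89.2 | 91.0 | 99.6 | 8.6 |
| | 0.5 | 86.2 | 94.9 | 99.6 | 4.7 |
| | 0.7 | 84.2 | 97.7 | 99.7 | 2.0 |
| | 0.9 | 81.1 | 99.5 | 99.7 | 0.2 |
| t(3) | 0.3 | 90.0 | 85.4 | 97.3 | 11.9 |
| | 0.5 | 87.6 | 87.2 | 96.1 | 8.9 |
| | 0.7 | 84.0 | 89.5 | 94.3 | 4.8 |
| | 0.9 | 80.6 | 92.8 | 94.1 | 1.3 |
| Normal | 0.3 | 90.7 | 74.0 | 88.0 | 14.0 |
| | 0.5 | 85.8 | 73.0 | 83.0 | 10.0 |
| | 0.7 | 80.5 | 72.9 | 77.9 | 5.0 |
| | 0.9 | 75.2 | 71.9 | 73.5 | 1.6 |

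Under no treatment difference, rejection rates were 4.3 to 5.6% for Wilcoxon and 4.5 to 5.6% for rank ANCOVA. The Monte Carlo standard error at 5% is √(0.05 × 0.95/4000) = 0.34 points. Quade's version of rank ANCOVA agreed within 0.2 points.

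**What the simulation does not cover.** Age had no effect on outcome, so the gains come from the baseline covariate alone and nothing here measures the cost of dropping the stratum. Outcomes were continuous, so heavily tied counts were not tested.

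**The case against.** The strongest reply is that little is lost. The SAP section is headed as supportive, its wording is permissive, and Wilcoxon is given as an example, so rank ANCOVA is already allowed. SAP 4.4.1.2 applies ANCOVA in any case. In the non-normal scenarios Wilcoxon power was already 85 to 99.5%, above the planned level of about 80%. Success under Protocol 9.2.3 requires only a trend. All of this stands, and it limits the consequence. It does not remove the point: one method is named, it is the one a programmer will run, and a better one uses data already collected.

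A reader might infer four stronger things that the documents do not support:

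- **That no effect estimate would be reported.** Protocol 9.3.2 and SAP 4.4.1.2 both require least squares mean differences with 95% CIs, and the Table 14.2.2.1 note adds the Wilcoxon p-value to them. Only an estimate matching the rank test is absent.
- **That the estimand switches from adjusted to unadjusted.** The adjusted ANCOVA comparison stays in the table.
- **That baseline is ignored.** The endpoint is change from baseline; baseline is subtracted but not used as a covariate.
- **That up to 14 power points are lost.** That figure comes from normal errors, where the fallback would not normally be called.

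The alternatives also have limits. Rank ANCOVA gives no difference in corneometer units, a van Elteren test stratified by age drops the baseline covariate, and the usual Hodges-Lehmann shift is unadjusted.

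**Conclusion.** The point holds for the fallback test only. The sole method named for a failed normality check omits both covariates of the main model, including the actual-age adjustment on which the SAP relies after the stratum errors. Where the fallback would apply, rank ANCOVA gained 0.2 to 11.9 power points over Wilcoxon, was ahead in every simulated cell, and kept type I error near 5%.

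The size rests on assumed correlations and error shapes, and on reading 0.6 SD as the SD of change. At a correlation of 0.9 the gain is 1.3 points or less under non-normal errors. The primary estimate and its CI are unaffected, and SAP 4.4 treats p-values mainly as summary statistics with no multiplicity control. This is a worthwhile, nearly free improvement rather than a defect that threatens the trial's conclusion.

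**What to change.** 1. In SAP 4.4.1.3 and 4.5.1, replace the Wilcoxon test with rank ANCOVA: ranked change on treatment and ranked baseline, with age stratum by actual age.
2. State that the ANCOVA least squares mean difference with 95% CI remains the lead estimate whatever the normality check shows. This also reconciles the alternative in Protocol 9.3.2 with the additive instruction in the SAP table shell.
3. Change the non-parametric rows of Table 14.2.2.1 and the matching secondary tables to the rank ANCOVA p-value. A Hodges-Lehmann shift with 95% CI may sit beside it, labelled as an unadjusted supplement.

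The cost is SAP wording and a few lines of code, with no new data. The downside is that the rank-based p-value has no estimate in corneometer units, which is why item 2 is needed. SAP Addendum 1 was requested after unblinding, so if the change is made at or after that stage it should be labelled post hoc.
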